## 7 MEASUREMENTS OF TREATMENT COMPLIANCE

Treatment compliance will be calculated for Part A, Part B and Part B post-flare separately. Part B summaries will not consider any post-flare escape treatment injection. There will be 2 approaches to calculate treatment compliance. The first will utilize the number of administered syringes and compare them to the scheduled expected number of injections. The sum of the difference in number of syringes between the actual used and expected syringes will be summarized. In addition, a ratio of compliance will be further computed based on the number of actual and expected syringes. The ratio of compliance will be summarized as a continuous variable and categorically ( $<0.80$ ,  $\geq 0.80$ – $\leq 1.0$  and  $>1.0$ ). The general formula for the compliance ratio (CR) is given as follows:

$$CR = \# \text{ actual syringes} / \# \text{ expected syringes}$$

The second approach defines compliance with study drug administration based upon comparing the actual day of administration with the expected day of administration. The expected day of administration will be based upon (1) the Baseline date and (2) the previous injection date. The

sum of the absolute difference in days between the actual and expected days will be summarized. In addition, a ratio of compliance will be computed based upon the actual and expected days for each of the 2 methods. The ratio of compliance will be summarized as a continuous variable and categorically ( $<0.80$ ,  $\geq 0.80$ ). The general formula for the compliance ratio is given as follows:

$$\text{Compliance Ratio (CR)} = \{[\text{Exposure Duration (days)}] - [\text{Cumulative Difference (days)}]\} / [\text{Exposure Duration (days)}]$$

The CR ranges between 0 and 1. Specific details are provided in Section 12.2.

Compliance based on these methods will be summarized by axSpA subpopulation and overall in Part A using the SS, by treatment group in Part B using the SSB and by treatment group in Part B Post-flare using the ETS. The compliance for Part B will be calculated based on the first injection in Part B and the compliance for Part B post-flare will be calculated based on the first injection in Escape Part.

If the Week 48 injection was not performed, the date of the Week 48 visit will be used as reference point for calculating the compliance of the first injection in Part B. Injections performed after the first injection in Part B will use the date of first injection in Part B as reference point for calculating the compliance of these injections.

If no Escape Week 0 injection was performed, the date of the Escape Week 0 visit will be used as reference point for calculating the compliance of the first injection in Escape Part. Injections performed after the first injection in Escape Part will use the date of first injection in Escape Part as reference point for calculating the compliance of these injections.

A by-subject listing of compliance will be provided by treatment group and axSpA subpopulation based on the SS.

## **8 EFFICACY ANALYSES**

Efficacy summaries for variables collected in Part A will be based on the OLS. All efficacy analyses for Part B will be performed using the RS, unless otherwise mentioned (ie, the FAS and PPS will be used for a sensitivity analysis on the primary endpoint only). Efficacy summaries for subjects experiencing a flare in Part B will be performed using the FS. All efficacy endpoints will be listed using the observed case data. Furthermore, for selected analyses, statistical appendices will be created and included in the CSR appendix “Documentation of Statistical Methods”.

### **8.1 Primary efficacy variable**

#### **8.1.1 Primary analysis of the primary efficacy variable**

The number and percentage of subjects in Part B who do not experience a flare will be summarized descriptively for the RS using NRI data. The 95% CI based on the Exact Binomial distribution will also be presented. Summary statistics will be presented by treatment group in Part B.

The primary analysis will be based on a logistic regression model which will include factors of treatment group, region, and mNY classification. The final values of the randomization stratification factors (region, mNY classification) will be used for this analysis. The odds ratios based on the proportion of subjects who do not experience a flare will be estimated from this

logistic regression model and presented with 95% 2-sided CIs and p-values. This analysis will be conducted for the RS using NRI data.

To avoid the problem of the monotone likelihood resulting in infinite large confidence intervals (eg, if one of the cell counts in the 2x2 table is equal to zero), a penalized maximum likelihood approach based on the modified score procedure of Firth (Heinze and Schemper, 2002) will be used in the logistic models.

Each CZP dose will be compared against PBO to establish superiority over PBO and will be tested sequentially at an alpha of 0.05. The primary statistical analysis of the primary efficacy variable will account for the testing of multiple doses by using a fixed sequence testing procedure. The predefined order of hypotheses testing, each at a 2-sided 0.05 significance level for the comparison between the given CZP dose and PBO, will be performed in the sequence shown below:

1. CZP 200mg Q2W vs PBO
2. CZP 200mg Q4W vs PBO

The second test will be performed irrespective of whether the first test is significant at the 0.05 level or not. However, the second test will be interpreted as statistically significant only if the first test is significant at the 0.05 level as well.

### **8.1.2 Secondary analyses of the primary efficacy variable**

The number and percentage of subjects in Part B who do not experience a flare will be summarized for the following subgroups: age, gender, race, region, baseline CRP level, overall ADAb status and mNY classification. Factors for subgroups and the interaction term of subgroup and treatment will be added to the primary model specified in Section 8.1.1. The 95% CI based on the Exact Binomial distribution will also be presented. These summaries will be performed for the RS using NRI data and will be based on descriptive statistics only.

### **8.1.3 Supportive and sensitivity analyses of the primary efficacy variable**

The number and percentage of subjects in Part B who do experience a flare will be summarized descriptively for the RS using NRI data, indicating the contributing event (ASDAS defined flare using scheduled visits only or using unscheduled visits, missing ASDAS values, premature study discontinuation with reason “AE or Lack of efficacy” or other reason, incorrectly ‘flared’ due to delay in data entry).

The flare by IXRS, calculated flare, time to flare and reason for flare according to NRI analysis will be listed based on the RS.

The analysis described in Section 8.1.1 will be repeated for the RS using the different approaches as defined in Section 3.2.22 (observed case, premature withdrawal, MMRM imputation, referenced-based multiple imputation). The 95% CI based on the Exact Binomial distribution will also be presented.

In addition, the analysis as described in Section 8.1.1 will also be repeated for the FAS and PPS using NRI data.

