### **2.4       Determination of sample size**

It is anticipated that approximately 210 subjects will be randomized in a 1:1:1 ratio to the CZP 200mg Q2W, CZP 200mg Q4W, and PBO treatment groups. The primary efficacy analysis is based on the proportion of subjects who do not experience a flare during Part B of the study. The proportion of subjects who do not experience a flare during Part B is assumed to be 80%, 75%, and 45% for the CZP 200mg Q2W, CZP 200mg Q4W, and PBO treatment groups, respectively. Given these assumptions, a sample size of 70 subjects per group provides 98% power to detect a significant difference between the CZP 200mg Q2W dose and PBO and 94% power to detect a significant difference between the CZP 200mg Q4W dose and PBO using a 2-sided significance level of 0.05.

Given that subjects enter Part B only if they have achieved sustained remission in Part A, it is necessary to estimate the number of subjects needed to enroll in Part A. It is assumed that approximately 28% of subjects enrolled in Part A will achieve sustained remission and qualify for Part B. This means that about 750 subjects will be enrolled in Part A in order to have 210 subjects who are randomized into Part B.

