### **3.2.22.4 Referenced based multiple imputation of ASDAS**

Missing data for the ASDAS scores at any visit in Part B up until Week 92 because of subject premature withdrawal, of subject experiencing a flare or of missing assessment at a given visit will be handled at each visit via reference based multiple imputation as described below:

This procedure will use an imputation model developed based on data from the PBO group only (Mallinckrodt, 2013). The reference-based multiple imputation assumes that the statistical behavior of the CZP and PBO-treated subjects after discontinuing study medication becomes that of the PBO-treated subjects. Data collected after discontinuation of the double-blind study treatment for both the CZP and PBO groups will be considered missing. Multiple imputations are used to replace missing outcomes for CZP- and PBO-treated subjects who discontinued using multiple draws from the posterior predictive distribution estimated from the PBO arm.

For subjects with a non-monotone (intermittent) missing pattern, Markov chain Monte Carlo (MCMC) will be used to impute their missing intermittent ASDAS scores by randomized treatment, geographic region and mNY classification. This will be done only once for each subject in order to provide a dataset with monotone missing (seed will be 221).

Data are processed sequentially by repeatedly calling SAS® PROC MI to impute missing outcome data at visits  $t=1, \dots, T$ , where  $t=1$  is Week 48 and  $t=T$  is Week 92

*Initialization.* Set  $t=1$  (Part B Baseline visit)

*Iteration.* Set  $t=t+1$ . Create a data set combining records from CZP- and PBO-treated subjects with columns for covariates (geographic region and mNY classification) and outcomes at visits 1 to  $t$ . Outcomes for all CZP-treated subjects are set to missing at visit  $t$  and set to observed or previously imputed values at visits 1 to  $t-1$ . Outcomes for PBO-treated subjects are set to observed at visit  $t$  or observed or previously imputed values at visits 1 to  $t-1$ .

*Imputation.* Run MCMC to impute missing values for visit  $t$  using previous outcomes for visits 1 to  $t-1$ , geographic region and mNY classification. Note that only PBO data will be used to estimate the imputation model since no outcome is available for drug-treated subjects at visit  $t$ .

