Repeat steps 2a-2d, 20 times with different seed values to create 20 imputed complete data sets (seeds will be 51, 52, 53, 54, 55, 56, 57, 58, 59, 510, 511, 512, 513, 514, 515, 516, 517, 518, 519, 520, 221).

*Analysis.* For each completed data set, the flare status will be calculated using the complete datasets (with no missing data). Analysis as described in [Section 8.1.1](#) will be performed in order to provide treatment odds ratios, 95% CIs and the p-values from the proc MIanalyze.

If there are not enough PBO subjects available at the visits to impute the missing ASDAS values at the visits in Part B so that the model converted, no data will be presented in the corresponding table.

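### Under reference-based multiple imputation, the arm-level exact binomial interval and the single fill of intermittent gaps each leave out part of the imputation variance

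*SAP*

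**What the plan says.** SAP Section 8.1.1 attaches the exact binomial interval to the descriptive result for each arm: "The number and percentage of subjects in Part B who do not experience a flare will be summarized descriptively for the RS using NRI data". Odds ratios come separately, from the logistic model.

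SAP Section 8.1.3 repeats that analysis under four approaches ("observed case, premature withdrawal, MMRM imputation, referenced-based multiple imputation") and then adds, without exception: "The 95% CI based on the Exact Binomial distribution will also be presented". Section 3.1 also promises exact binomial intervals for the primary variable and makes no exception for multiple imputation.

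SAP Section 3.2.22.4 sets out the imputation in two stages. Intermittent gaps are filled by MCMC: "This will be done only once for each subject in order to provide a dataset with monotone missing (seed will be 221"). The remaining monotone missing values are then imputed "20 times with different seed values to create 20 imputed complete data sets". For pooling, it provides "treatment odds ratios, 95% CIs and the p-values from the proc MIanalyze". It gives no pooling rule for the arm percentages.

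**The concern.** Three of the four approaches yield one flare status per subject and so one whole-number count per arm, to which an exact interval can be applied. Reference-based multiple imputation yields 20 counts per arm, and their average need not be a whole number. The exact interval is then undefined as specified. If it is computed from the average or from one chosen data set, it reflects sampling variance only.

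The once-only fill is a separate matter. All 20 data sets share the same filled values, so those values contribute nothing to the between-imputation variance. That part of the uncertainty is lost from every interval, including the pooled odds-ratio interval.

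Section 4.2 says the sensitivity analyses exist to test the robustness of the NRI result. Intervals that leave out part of the missing-data uncertainty serve that purpose less well.

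**Working it through.** **Inputs from the SAP.** 70 subjects per arm (Section 2.4); the flare-free proportion "is assumed to be 80%, 75%, and 45% for the CZP 200mg Q2W, CZP 200mg Q4W, and PBO treatment groups, respectively"; M = 20 imputations (Section 3.2.22.4).

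**Assumptions, not in the SAP.**
- m: share of an arm whose flare status rests on imputed ASDAS, 5-30%.
- q: probability that such a subject is imputed flare-free, from 45% (placebo-like) to the arm's own rate.
- g: share whose status turns on an intermittent gap, 2-5%, with 10% as an extreme.

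A binary approximation stands in for the ASDAS imputation.

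**Step 1: the plan's own power.** Two proportions, pooled null variance, continuity correction: z = (d - 1/n - 1.96 × se0)/se1.
- Q2W vs PBO: (0.35 - 0.0143 - 1.96 × 0.0818)/0.0763 = 2.30, power 98.9% (stated 98%).
- Q4W vs PBO: (0.30 - 0.0143 - 1.96 × 0.0828)/0.0788 = 1.57, power 94.1% (stated 94%).

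Both agree with the plan, and neither depends on this point.

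**Step 2: exact interval.** Q2W, 56/70: 68.7% to 88.6%, width 19.89 points. PBO: 0.45 × 70 = 31.5, which is not a count; with 32/70 the interval is 33.7% to 58.1%, width 24.31 points.

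**Step 3: Rubin interval for one arm.**
- W = p(1-p)/n
- B = [m + m²/(1-m)] × q(1-q)/n (random draws, plus estimation of q)
- T = W + (1 + 1/20)B
- r = 1.05B/W, df = 19(1 + 1/r)²
- width = 2 × t × √T

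Example, Q2W, m = 20%, q = 45%: W = 0.16/70 = 0.002286; B = 0.25 × 0.2475/70 = 0.000884; T = 0.003214; r = 0.406; df = 228; t = 1.970; width = 2 × 1.970 × 0.0567 = 22.34 points, or 1.123 times the exact width.

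| m | Q2W pooled width (q = 80% to 45%) | pooled/exact | PBO pooled width (q = 45%) | pooled/exact |
|---|---|---|---|---|
| 5% | 19.26-19.53 | 0.968-0.982 | 23.95 | 0.985 |
| 10% | 19.82-20.39 | 0.997-1.025 | 24.65 | 1.014 |
| 20% | 21.12-22.34 | 1.062-1.123 | 26.26 | 1.080 |
| 30% | 22.71-24.67 | 1.142-1.241 | 28.24 | 1.162 |

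At 20% the pooled Q2W interval is 6-12% wider than the exact one. Put the other way, the exact interval is 1 - 1/1.062 = 6% to 1 - 1/1.123 = 11% narrower. If only the random-draw part of B is kept, with q = 75%, then T = 0.002286 + 1.05 × 0.2 × 0.1875/70 = 0.002848, the width is 20.97 points and the exact interval is 5% narrower.

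The logit scale gives the same answer. For the example, logit(0.8) = 1.386, SE = 0.0567/0.16 = 0.354, and 1.386 ± 1.970 × 0.354 back-transforms to 66.6% to 88.9%, width 22.4 points.

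**Step 4: single fill.** Take q = p and treat the two sources as additive. Since m + m²/(1-m) = m/(1-m), the ratio of SE with a single fill to SE with all variance is √{[1 + 1.05m/(1-m)] / [1 + 1.05m/(1-m) + 1.05g/(1-g)]}.
- m = 20%, g = 2%: √(1.2625/1.2839) = 0.992.
- m = 20%, g = 5%: √(1.2625/1.3178) = 0.979.
- m = 10%: 0.991 at g = 2% and 0.976 at g = 5%.
- g = 10%: 0.952 (m = 10%) and 0.957 (m = 20%).

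The SE is therefore about 1-2% too small for g of 2-5%, and 4-5% too small at g = 10%.

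**The case against.** The strongest reply is that inference in this analysis is already pooled. Section 3.2.22.4 runs the model on each completed data set and combines the results: the analysis "will be performed in order to provide treatment odds ratios, 95% CIs and the p-values from the proc MIanalyze". A reader might infer that all error bars of the multiple-imputation analysis ignore imputation uncertainty. The SAP does not support that: the treatment comparison includes the variance from the 20 monotone imputations and lacks only the intermittent part. Withdrawal and post-flare gaps, which are monotone, are covered.

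A reader might also fear that the 20 data sets will be stacked and counted as if they were separate subjects. No section calls for this, and the rule of analysing each data set and then combining points the other way.

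The exact interval is descriptive and conservative at n = 70. At 5% imputed it is slightly wider than the pooled interval, and at 10% about equal, so it is not always too narrow. A filled gap changes flare status only if it exceeds 3.5 or completes two consecutive values of at least 2.1 (Section 3.2.22), so g should be well below the share of subjects with any gap. Finally, this is one of four alternative approaches, and Section 3.2.22.4 even allows the table to stay empty.

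All of this stands and keeps the point small. It does not remove the point: the interval prescribed in 8.1.3 has no count to work on under this approach, and the once-only fill is an explicit rule, not a missing detail.

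**Conclusion.** Wrong as written, low severity: a correction the sponsor could make, not one on which a conclusion depends. Two stated rules omit imputation variance: the exact binomial interval for the arm percentages, and the shared fill of intermittent gaps.

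The interval is affected noticeably only when a larger share of subjects is imputed: roughly 5-12% too narrow at about 20%, and close to neutral at 10% or less. The single fill costs about 1-2% of the SE under the assumed gap shares. These sizes rest on assumed values of m, q and g and on a binary approximation; the direction of the omission does not. The fixed-sequence test on NRI data, its alpha and the power of the trial are untouched.

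**What to change.** In Section 8.1.3, state that under reference-based multiple imputation the arm-level flare-free proportions and their 95% CIs are pooled over the 20 data sets by Rubin's rules on the logit scale, in place of the exact binomial interval. Keep the exact interval for the other three approaches.

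In Section 3.2.22.4, draw 20 monotone data sets in the MCMC step and run one reference-based chain from each. List exactly 20 chain seeds: the present list has 9 (51 to 59) + 11 (510 to 520) + 1 (221) = 21 entries, and 221 is also the seed of the MCMC step.

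The cost is a few words of SAP text and small programming changes. The arm-level intervals will be somewhat wider if many subjects are imputed and about the same, or slightly narrower, if few are.

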## **8.2 Secondary efficacy variables**

### **8.2.1 Part A**

All summaries of secondary efficacy variables in Part A will be based on the OLS.

#### **8.2.1.1 Percentage of subjects achieving sustained remission at Week 48**

The number and percentage of subjects achieving sustained remission at Week 48 will be summarized in frequency tables by axSpA subpopulation and for all subjects combined. The 95% CI based on the Exact Binomial distribution will also be presented. The presentation will be done on the observed case data and will be repeated on the imputed data using NRI.

#### **8.2.1.2 ASDAS disease activity (ASDAS-ID, ASDAS-LD, ASDAS-HD and ASDAS-vHD) at Week 48**

ASDAS disease activity at Week 48 will be summarized in frequency tables by axSpA subpopulation and for all subjects combined. The number and percentage of subjects in each of the 4 disease activity levels will be presented.

The presentation will be done using observed case data and will be repeated using LOCF imputation for the missing data.

#### **8.2.1.3 ASDAS clinical improvement (ASDAS-MI and ASDAS-CII) at Week 48**

The number and percentage of subjects achieving ASDAS-MI and ASDAS-CII at Week 48 will be summarized in frequency tables by axSpA subpopulation and for all subjects combined. The presentation will be done using observed case data and will be repeated using NRI data.

### **8.2.2 Part B**

The following analyses are not part of the multiplicity-controlled testing procedure described in Section 8.1. The p-values reported for these analyses will not be adjusted for multiplicity and will be considered nominal. All analyses and summaries of the efficacy variables in Part B will be based on the RS. All tables will be presented by treatment group in Part B.

#### **8.2.2.1 Time to flare**

The time to flare will be analyzed using Kaplan-Meier methods, comparing each CZP dose to PBO. Stratified two-sided log rank test using strata geographic region (North America, Western Europe, Eastern Europe and Asia) and mNY classification (mNY positive, mNY negative) will be used to evaluate between-group differences.

Kaplan-Meier plots of the time to flare will also be produced. Kaplan-Meier estimates of percentages of subjects experiencing a flare by Week 52, Week 56, Week 60, Week 64, Week 68, Week 72, Week 76, Week 80, Week 84, Week 88, Week 92 and Week 96 will be provided along with the corresponding 95% CI by treatment arm. For the calculation of the 95% CI, the LOGLOG transformation will be used.

These analyses will be repeated using the different approaches as defined in Section 3.2.23 (observed case, premature withdrawal).

### **8.2.2.2 Continuous secondary efficacy variables**

Summary statistics of observed and change from Part B Baseline to Week 96 values for ASDAS, BASDAI, BASFI, and BASMI will be presented by treatment group. These summary statistics will be repeated for Part A Baseline.

The changes from Part B Baseline to Week 96 in ASDAS, BASDAI, BASFI and BASMI will be compared between treatment groups using a MMRM. The pattern of missingness for these variables is assumed to be MAR. Post-flare data for subjects experiencing a flare (in any treatment group) will be treated as missing in the MMRM analysis. The MMRM methods will be applied to all observed change from Part B Baseline data obtained from Week 48 up to Week 96. The model will include Part B Baseline score as a fixed-effect covariate, treatment group, region, mNY classification, and visit as fixed-effect categorical factors, and Part B Baseline-by-visit and treatment group-by-visit as interaction terms. The multiple visits for each subject will be incorporated as repeated measures (fixed term) within each subject (random term). An unstructured covariance matrix will be used and visit will be treated as a categorical predictor. An unstructured correlation pattern will be used to estimate the variance-covariance of the within-subject repeated measures. Summary tables will present the adjusted means for PBO and the CZP doses, the respective differences to PBO, the corresponding p-values, and 95% CIs.

The comparison between treatment groups using MMRM will be repeated for Part A Baseline with Part A Baseline score as a fixed-effect covariate, treatment group, region, mNY classification, and visit as fixed-effect categorical factors, and Part A Baseline-by-visit and treatment group-by-visit as interaction terms.

Summary statistics of observed and change from Part B Baseline to Week 96 values for SIJ SPARCC and Spine ASspiMRI-a in the Berlin modification scores will be presented by treatment group. These summaries will be based on observed case data.

The changes from Part B Baseline in SIJ SPARCC and spine ASspiMRI-a in the Berlin modification scores at Week 96 will be compared between treatment groups using an analysis of covariance (ANCOVA) model. The model will include Part B Baseline score, treatment group, region, and mNY classification. Summary tables will present the adjusted means for PBO and the CZP doses, the respective differences to PBO, the corresponding p-values, and 95% CIs. This analysis will be performed using observed case data only.

These summary statistics will be repeated for Part A Baseline and the model includes Part A Baseline score, treatment group, region, and mNY classification.

